### **Duration of Treatment-emergent Injection Site Reaction (ISR)**

Duration = (min (ISR end date, EOS date) – ISR start date) + 1.

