3.2.3 Risk Assessment

The most common adverse events experienced by subjects included mild (grade 1) painless erythema at or near the injection site, sometimes accompanied by pruritus, that was self-resolving. As of 22 September 2020, 2 serious hypersensitivity reactions to efavaleukin alfa have been reported. The 2 events (grade 2 and 3, respectively)

occurred within the first 24 hours after initial dose and resolved without sequelae with symptomatic treatment (ie, systemic corticosteroids). More detailed information about the safety risks of efavaleukin alfa may be found in the Investigator's Brochure.

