### **8.3.2 Safety**

The following imputation for missing or incomplete data will be performed if required:

Incomplete or missing start/stop dates for adverse event and concomitant medication will be imputed as described in [Appendix A](#).

Laboratory measurements that are below the lower quantification limits will be considered equal to the lower limit of quantification for all analyses unless explicitly noted otherwise. PD data that are below the lower limit of quantification will be considered equal to half of the lower limit of quantification for all analyses unless specified otherwise. PD data that are above the upper quantification limits will be considered equal to the upper limit of quantification for all analyses unless specified otherwise.

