### **Overall summary of subject incidence of treatment-emergent adverse events and**

by preferred term and worst severity grade will be provided by anti-AMG592 and [REDACTED] status. Subject incidence of events of interest (standardized MedDRA queries and/or Amgen Medical Queries) will also be summarized according to their categories, preferred term, and worst severity grade. Events of interest could include but are not limited to Hypersensitivity, Tachyarrhythmias, Tachypnea, Hematopoietic Cytopenia, **Eosinophilic Disorder**, Leucocyte Changes, Infection and Infestation, Cytokine Release Syndrome, **Drug Related Hepatic Disorder**, and Injection Site Reaction. Number of episodes and duration of treatment-emergent injection site reactions will be further summarized.

Subject incidence of treatment-emergent adverse events identified by COVID-19 standardized MedDRA queries and serious adverse events occurring on or after the COVID-19 infection will also be summarized.

Subject incidence of disease related events and fatal disease-related events will be tabulated by system organ class and preferred term. They are defined for this study in [Appendix D](#).

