### Imputation Rules for Partial or Missing Stop Dates

Initial imputation

- If the month and year are present, impute the last day of that month.
- If only the year is present, impute December 31 of that year.
- If the stop date is entirely missing, assume the event or medication is ongoing.

If the imputed stop date is before the start date, set stop date to missing.

---

If the imputed stop date is after the death date, impute as death date.

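### Injection-site reactions that are unresolved or have no stop date are given a duration running to End of Study and summarised as if observed, with a default summary that omits the median

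*SAP*

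**What the plan says.** SAP 5.5 gives the ISR formula as "Duration = (min (ISR end date, EOS date" minus the ISR start date, plus 1. It has no indicator separating a reaction that ended from one cut off at EOS. SAP 9.6.2 commits to reporting the result: "Number of episodes and duration of treatment-emergent injection site reactions will be further summarized". It names neither the statistic nor whether the unit is the episode or the subject.

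SAP 8.3.2 sends adverse-event dates to Appendix A: "Incomplete or missing start/stop dates for adverse event and concomitant medication will be imputed as described in" that appendix. Four rules there matter:

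- No stop date: "If the stop date is entirely missing, assume the event or medication is ongoing".
- Month and year only: "If the month and year are present, impute the last day of that month".
- Year only: "If only the year is present, impute December 31 of that year".
- Inconsistent result: "If the imputed stop date is before the start date, set stop date to missing".

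SAP 5.2 sets a subject's EOS at the last protocol-specified procedure. By plan this is the safety follow-up visit, 6 weeks (± 3 days) after the last dose.

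For continuous data, SAP 9.1 lists mean, standard deviation, minimum, maximum and n. Protocol 10.4.2.1 lists the median as well. SAP section 10, on changes from the protocol, does not mention dropping it.

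**The concern.** A reaction still present at EOS, or never given a stop date, has an unknown duration. All that is known is a lower bound (if unresolved) or nothing beyond the start (if undated). The formula turns both into exact values and pools them with reactions whose end was seen. The value assigned depends on how long the subject stayed in the study, not on the reaction. Partial stop dates are moved to the latest day they allow, which lengthens durations in one direction only.

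Protocol 3.2.3 includes among the most common adverse events "mild (grade 1) painless erythema at or near the injection site, sometimes accompanied by pruritus, that was self-resolving". Short true durations with an occasional very long assigned value make a right-skewed variable, for which mean, SD and maximum are the fragile statistics. One undated record could make the table appear to contradict the self-resolving description. Because the artefact grows with follow-up, it can also differ between dose levels whose subjects were followed for different lengths of time.

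The SAP deals with skew elsewhere: pharmacodynamic data are log-transformed (9.7.1.2) and pharmacokinetic parameters get a median (9.7.1.1). ISR duration gets neither.

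**Working it through.** **The plan's own figure.** The documents state no ISR duration, but Protocol 5.3.2 gives maximum participation, which bounds the distance to EOS. Screening 28 days + treatment + follow-up 42 days:

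- 52 weeks: 28 + 364 + 42 = 434 days; 434 / 30.44 = 14.3 months (stated: about 14).
- 260 weeks: 28 + 1820 + 42 = 1890 days; 1890 / 30.44 = 62.1 months (stated: up to 62).

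Both are reproduced, so the planned timeline is read correctly.

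**Planned EOS day**, with week w = Day 7w + 1 and EOS = last dose + 42:

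- Q2W, last dose week 50: Day 351; EOS Day 393.
- QW, last dose week 51: Day 358; EOS Day 400.

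**Duration given to an ISR with no stop date:**

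- Start Day 1: 393 − 1 + 1 = 393 days (Q2W) or 400 − 1 + 1 = 400 days (QW).
- Start at last dose: 42 + 1 = 43 days in either schedule.

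**Effect on the mean.** Assumptions, since the documents give neither figure: every true duration is 5 days, and one of n episodes is an undated Day 1 ISR. The mean is ((n − 1) × 5 + D) / n and the rise is (D − 5) / n, with D = 393 or 400.

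| Episodes n | Q2W mean (rise), days | QW mean (rise), days |
|---|---|---|
| 3 | 134.3 (129.3) | 136.7 (131.7) |
| 6 | 69.7 (64.7) | 70.8 (65.8) |
| 10 | 43.8 (38.8) | 44.5 (39.5) |
| 30 | 17.9 (12.9) | 18.2 (13.2) |
| 100 | 8.88 (3.88) | 8.95 (3.95) |

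The maximum is 393 or 400 days whatever n is. The median is 5 days in every row. The result hardly depends on the assumed true duration: at n = 10, using 1 or 14 days in place of 5 gives a rise between 37.9 and 39.9 days.

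**Partial dates.** A year-only stop for a reaction that really ended on 1 January becomes 31 December, up to 364 days too long in a non-leap year. A month-only stop can be up to 30 days too long. Both are still capped at EOS.

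**What censoring would do.** Take the 10-episode Q2W case, with the undated ISR censored at Day 393. The Kaplan-Meier curve falls to 0.1 at 5 days, so its median is 5 days. A mean restricted to 393 days is 5 + 0.1 × 388 = 43.8 days, the same as the simple mean. Censoring therefore helps only if the median is the reported statistic.

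**The case against.** The other side has four serious arguments.

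1. **Missing dates should be rare.** Protocol Appendix 4 requires onset and resolution dates. Protocol 9.2.3.1.3 requires follow-up to resolution or stabilisation, subjects are seen weekly or every two weeks, and SAP 7.2 expects data issues to be settled before the final lock. This stands as a limit on frequency, and no rate of missing dates is given. It does not remove the problem: follow-up may end at stabilisation or loss to follow-up, and a truly unresolved ISR remains unobserved however clean the data are.

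2. **The median may be reported anyway.** SAP 9.1 introduces its list as inclusive, the protocol lists the median, and a reported maximum would expose an extreme value. True, but nothing requires the median for ISR duration, and the maximum does not say whether the value was observed.

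3. **It is a supplementary summary.** The phase 1b part has no statistical hypothesis, and ISR incidence, grade and episode count do not use the formula. This stands, and it sets the priority.

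4. **The remedies have weaknesses.** Kaplan-Meier over episodes ignores repeated reactions within a subject, and a summary of complete dates only favours short reactions. Both stand and are allowed for in the fix.

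A reader might infer that one missing stop date adds hundreds of days to the mean. The arithmetic does not support that in general: hundreds of days describes the single episode or the maximum. In the 52-week period, a rise in the mean of 100 days or more needs 3 episodes or fewer (388 / 3 = 129; 395 / 4 = 99).

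A reader might also infer that every incompletely dated ISR runs to EOS. Appendix A sends partial dates to month end or 31 December. They reach EOS only if that date is on or after EOS, or falls before the start and is reset to missing.

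**Conclusion.** The point holds as a modest defect in a descriptive safety summary. As written, the SAP gives an ISR that is unresolved or wholly undated its full span to EOS and summarises it as observed, by statistics that are not robust to it. In the 52-week period one such Day 1 reaction moves the mean by about 4 days over 100 episodes, 13 over 30 and 39 to 40 over 10. It sets the maximum and leaves the median unchanged.

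These sizes rest on an assumed 5-day true duration, assumed episode counts, a Day 1 start and dosing to plan. A later start or earlier discontinuation makes them smaller.

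Longer spans arise only in extended dosing. Dosing to week 259 would put EOS at Day 1814 + 42 = 1856, but that should not be taken as a typical case: the SAP states that the study was terminated early, and the documents do not show that any subject reached that week.

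**What to change.** Amend SAP 5.5 and 9.6.2 as follows:

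- Flag ISRs that are unresolved or have no stop date as censored at EOS, and report their number separately by dose level.
- Report median and quartiles of duration instead of relying on the mean. If a Kaplan-Meier median per episode is used, state that episodes repeat within a subject. Do not substitute a restricted mean.
- State whether the unit is the episode or the subject.
- Identify ISRs whose stop date was imputed from a partial date, and show the summary with and without them. Any summary restricted to complete dates should be supportive only, because it favours short reactions.

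The cost is a paragraph of SAP text and slightly more programming. No new data are needed.

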## **5.6 Demographic and Baseline Characteristics**

### **Age**

Age in years at the screening visit, which is collected in the eCRF.

### **Duration of cGVHD**

Number of years from date of diagnosis of cGVHD (collected in chronic GVHD medical history eCRF) to the date of Study Day 1.

## **Duration of steroid refractory cGVHD**

Number of years from date of diagnosis of steroid refractory cGVHD (collected in chronic GVHD medical history eCRF) to the date of Study Day 1.

### **6. Analysis Sets**

#### **6.1 Safety Analysis Set**

The safety analysis set is defined as all subjects who have received at least 1 dose of efavaleukin alfa in the study. All analyses will be conducted on the safety analysis set unless noted otherwise.

#### **6.2 DLT Analysis Set**

The analysis of DLT will be restricted to DLT analysis set which consists of DLT-evaluable subjects in the study. The DLT evaluation period for each subject is 4 weeks from the first dose of efavaleukin alfa. To be evaluable for a DLT, subjects must have received at least 2 doses of efavaleukin alfa, or have experienced a DLT within the DLT evaluation period.

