7.4 Dose Modification

7.4.1 Phase 1b Dose-cohort Study Escalation/De-escalation

7.4.1.1 Dose Level Review Meetings

After all DLT-evaluable subjects within a cohort have completed the 4-week DLT evaluation period, a DLRM will be held to review data, monitor safety, and make dose change decisions. See [Appendix 3](#) for more details on the DLRM.

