7.4.1.2 Definition of Dose Limiting Toxicities for Phase 1b

The DLT evaluation period for each subject is 4 weeks from the first dose of efavaleukin alfa. To be evaluable for a DLT subjects must have received at least 2 doses of efavaleukin alfa or have experienced a DLT within the DLT evaluation period. All subjects who experience a DLT will discontinue study therapy and complete safety follow-up. Dose limiting toxicity events will be used to guide dose escalation decisions and to determine the MTD as described in Section 5.1.1.

The following DLT criteria apply only to the phase 1b part of the study:

- Non-hematological toxicity \geq grade 4 related to efavaleukin alfa. Non-hematological laboratory abnormalities without clinical significance will not be considered DLTs (based upon the investigator's discretion in conjunction with Amgen).
- Hematological toxicity \geq grade 4 related to efavaleukin alfa defined as decreases in peripheral counts (ANC or platelets) persisting longer than 72 hours, as measured by 2 separate results, that are not related to malignant disease relapse, infection, or other etiologies.
- Constitutional events (ie, fever, fatigue) \geq grade 3 that are classified as serious adverse events by the investigator and related to efavaleukin alfa.

- Infection: Infection is considered an expected complication of cGVHD and its treatment. cGVHD itself increases the risk of infection, including life-threatening infection. Therefore only grade 4 or 5 infections considered by the investigator to be related to efavaleukin alfa will be reviewed by the DLRM to determine whether the infection is considered a DLT.

Subjects who develop an uncontrolled grade 4 life-threatening infection (eg, sepsis, ARDS), as assessed by the investigator, will discontinue efavaleukin alfa and remain in the study for safety follow-up (see Section 9.1.5).

After completing the 4-week DLT evaluation period, phase 1b subjects will be evaluated by standard safety reporting.

[figure not shown]

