10.2 Analysis Sets, Subgroups, and Covariates

10.2.1 Analysis Sets

Phase 1b

- Safety Analysis Set: The safety analysis set is defined as all subjects who have received at least 1 dose of efavaleukin alfa in phase 1b portion of the study. All phase 1b analyses will be conducted on the safety analysis set unless noted otherwise.
- DLT Analysis Set: The analysis of DLT will be restricted to DLT analysis set which consists of DLT-evaluable subjects in the phase 1b portion of the study. The DLT evaluation period for each subject is 4 weeks from the first dose of efavaleukin alfa. To be evaluable for a DLT subjects must have received at least 2 doses of efavaleukin alfa or have experienced a DLT within the DLT evaluation period.

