## **2. Objectives, Endpoints and Hypotheses**

### **2.1 Objectives and Endpoints**

Objectives	Endpoints
Primary	

• To evaluate the safety and tolerability of multiple ascending doses of efavaleukin alfa in subjects with steroid refractory chronic graft versus host disease (cGVHD)

	

• Incidence of dose limiting toxicities (DLTs) at first 4 weeks

• Incidence of all treatment-related and treatment-emergent adverse events and serious adverse events

Secondary	
Exploratory	

Objectives	Endpoints

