### **Dose Limiting Toxicity (DLT)**

The DLT evaluation period for each subject is 4 weeks from the first dose of efavaleukin alfa. To be evaluable for a DLT, subjects must have received at least 2 doses of efavaleukin alfa, or have experienced a DLT within the DLT evaluation period. All subjects who experience a DLT will discontinue study therapy and complete safety follow up. Dose limiting toxicity events will be used to guide dose escalation decisions and to determine the maximum tolerated dose as described in Section [3.1](#).

These events will be marked as DLT on Events eCRF.

[figure not shown]
The following DLT criteria apply to the study:

[figure not shown]
- Non-hematological toxicity  $\geq$  grade 4 related to efavaleukin alfa. Non-hematological laboratory abnormalities without clinical significance will not be considered DLTs (based upon the investigator's discretion in conjunction with Amgen).
- Hematological toxicity  $\geq$  grade 4 related to efavaleukin alfa defined as decrease in peripheral counts (ANC or platelets) persisting longer than 72 hours, as measured by 2 separate results, that are not related to malignant disease relapse, infection, or other etiologies.
- Constitutional events (i.e., fever, fatigue)  $\geq$  grade 3 that are classified as serious adverse events by the investigator and related to efavaleukin alfa.
- Infection: Infection is considered an expected complication of cGVHD and its treatment. cGVHD itself increases the risk of infection, including life threatening infection. Therefore only grade 4 or 5 infections considered by the investigator to be related to efavaleukin alfa will be reviewed by the DLRM to determine whether the infection is considered a DLT.

[figure not shown]
Subjects who develop an uncontrolled grade 4 life threatening infection (e.g., sepsis, ARDS), as assessed by the investigator, will discontinue efavaleukin alfa and remain in the study for safety follow-up (see Section 5.4) after completing the 4-week DLT evaluation period, subjects will be evaluated by standard safety reporting.

[figure not shown]
2014 cGVHD NIH response Consensus criteria algorithm (NIH Form A - 2014)

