#### 9.6.2.1 Dose Limiting Toxicities

The analysis of the probability of DLT will be based on the Dose Escalation part of the study defined in Section [3.1](#). A listing and summary of the subject incidence of DLT will be provided should they occur. After there is at least 1 DLT observed at any dose level, a Bayesian logistic regression model (BLRM) ([Bailey et al, 2009](#); [Neuenschwander et al, 2008](#)) will be used to inform dose escalation and the results of this analysis will be provided to the each DLRM. Three toxicity probability intervals (TPI) of DLT will be defined: target TPI (20% to 30%), excessive TPI (30% to 60%) and unacceptable TPI (60% to 100%). Adverse events meeting DLT criteria after week 4 and PD information may also be included in the model, as available. The model will recommend an MTD as the dose with highest probability in the target TPI, but with less than 25% probability in excessive TPI or unacceptable TPI. Lower dose levels, intermediate dose levels, or alternative dosing schedules may be considered based on all available information as long as they do not exceed the estimated MTD per the model.

Let  $\mathbf{d} = (d_1, \dots, d_k)$  denote the vector of all efavaleukin alfa doses to be studied in the study. The probability of a DLT at dose level  $d_i, i=1, \dots, k$  is assumed to follow a Bernoulli distribution with probability  $p_i$  where the logit of  $p_i$  increases linearly with the log of the standardized dose in the following 2-parameter logistic model:

$$\log \left[ \frac{p_i}{1 - p_i} \right] = \text{logit}(p_i) = \log[a] + \exp(\log[b]) \log\left(\frac{d_i}{\max(\mathbf{d})}\right)$$

where a and b are random variables and  $d_i$  is dose level represented by predicted

[REDACTED]  $d_k$  is an additional dose assuming Treg concentration = [REDACTED] that's higher than the currently planned doses. Thus  $\mathbf{d} = [REDACTED]$ . If additional dose cohorts were added during study conduct (e.g., decision following a DLRM), the value of  $\mathbf{d}$  will be updated.

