The probability of each TPI and of a DLT will be summarized by dose along with the estimated dose-toxicity curve. A final estimate of the MTD will be estimated from the Bayesian model by utilizing all DLT-evaluable subjects. Please refer to [Appendix C](#) for more details on the BLRM and its operation characteristics. Before each DLRM, the above BLRM will be fitted with the prior distribution as specified in [Appendix C](#). This model will only be used to aid DLRM dosing decision thus the recommendation of the model is non-binding in nature.

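### The DLT set counts a subject without a DLT as evaluable after two doses, without observation through week 4, so early losses enter the 4-week DLT incidence as full non-DLTs (minor)

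*SAP*

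**What the plan says.** The primary endpoint in SAP 2.1 is "Incidence of dose limiting toxicities (DLTs) at first 4 weeks". Protocol 7.4.1.2 fixes the window: "The DLT evaluation period for each subject is 4 weeks from the first dose of efavaleukin alfa".

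Who counts in that endpoint is defined in four places with the same content. SAP 6.2 says "subjects must have received at least 2 doses of efavaleukin alfa, or have experienced a DLT within the DLT evaluation period". SAP 5.5, under Dose Limiting Toxicity, says "To be evaluable for a DLT, subjects must have received at least 2 doses of efavaleukin alfa, or have experienced a DLT". Protocol 10.2.1 says "To be evaluable for a DLT subjects must have received at least 2 doses of efavaleukin alfa", again with a DLT in the window as the alternative, and Protocol 7.4.1.2 repeats this. None of the four adds that a subject without a DLT must be observed until the window closes.

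SAP 9.6.2.1 applies this set to the model. The DLT outcome at each dose "is assumed to follow a Bernoulli distribution with probability" p, with no weight described for partial follow-up, and "A final estimate of the MTD will be estimated from the Bayesian model by utilizing all DLT-evaluable subjects".

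The text on dose level review meetings assumes more than the definition requires. Protocol 7.4.1.1 says "After all DLT-evaluable subjects within a cohort have completed the 4-week DLT evaluation period, a DLRM will be held to review data". Protocol Appendix 3 and SAP 7.1 give matching timing.

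**The concern.** The endpoint is a 4-week risk, but membership of its denominator is settled at dose 2. A subject who leaves the study on day 10 without a DLT is recorded as DLT-free for a period in which nobody looked. Under the rule as written the error has one direction. Every DLT in the window counts whichever denominator is used, so counting partly observed subjects as negatives can only leave the rate unchanged or lower it. For a primary safety endpoint in cohorts of 3 to 6, that is the unfavourable direction.

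Nothing else in the documents removes such a subject from the set. Replacement of subjects with fewer than 4 doses (Protocol 5.2.1, SAP 3.2.1) is optional and says nothing about the analysis set. Protocol 8.2 keeps data up to withdrawal of consent. SAP 8.3 does not address partial DLT follow-up. Disposition with reasons (SAP 9.2) is split at week 52 and the extension, so it would not show how many of the reported non-DLTs were only partly observed.

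**Working it through.** **Inputs from the documents.** Window of 28 days; weekly or 2-weekly dosing, so dose 2 is nominally on day 8 or day 15; cohorts of 3 to 6 evaluable subjects (SAP 3.1). BLRM prior (SAP Appendix C): log a has mean -1.283 and SD 1.002, log b has mean 0.280 and SD 0.770, correlation -0.568. Overdose limit 0.25, read here as the probability that the DLT rate exceeds 30%.

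**Assumptions.** The documents give no early-loss count and no DLT timing. I assume loss is unrelated to DLT risk, and I vary the timing.

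**Check of the plan's own figure.** At the maximum dose, logit(p) = log a, so P(p ≤ 0.5) = Φ(1.283/1.002) = 0.900. Appendix C states 0.90, so the prior reproduces.

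**Step 1: when the reported rate moves.** With x DLTs among n counted subjects, m of them lost without a DLT, the rule gives x/n; leaving the lost subjects out gives x/(n-m).
- x = 0: 0/6, 0/5 and 0/4 are all 0%, so nothing changes.
- x = 1: 1/6 = 16.7%, 1/5 = 20.0%, 1/4 = 25.0%.

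A shift needs a DLT and a loss in the same cohort.

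**Step 2: expected incidence under the plan's rule.** Let R be the true 4-week risk, q the chance of a DLT before loss, and k the number of 6 who leave at that point. Expected rate = [(6-k)R + kq]/6. Under a constant hazard q = 1-(1-R)^(t/28). For R = 0.25 and t = 8, q = 1-0.75^(8/28) = 0.0789, which is 32% of R.
- k = 1: (5 × 0.25 + 0.0789)/6 = 22.1%.
- k = 2: (4 × 0.25 + 2 × 0.0789)/6 = 19.3%.

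**Step 3: expected incidence with partly observed non-DLTs left out.** Expected rate = sum over j of C(k,j) q^j (1-q)^(k-j) × [(6-k)R + j]/(6-k+j), where j of the k had a DLT before leaving and so stay in. For k = 1, t = 8: 0.9211 × 0.25 + 0.0789 × 2.25/6 = 26.0%.

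| True risk 25%, cohort of 6 | Plan's rule, 1 / 2 lost | Losses left out, 1 / 2 lost |
|---|---|---|
| Constant hazard, loss after day 8 | 22.1% / 19.3% | 26.0% / 27.3% |
| Constant hazard, loss after day 15 | 23.2% / 21.4% | 26.8% / 29.2% |
| 70% of risk by day 8 (assumed) | 23.8% / 22.5% | 27.2% / 30.1% |
| 10% of risk by day 8 (assumed) | 21.3% / 17.5% | 25.3% / 25.8% |

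The plan's rule errs low and the alternative errs high. In every case computed, the two expected rates lie on either side of 25%. With a constant hazard and loss after day 8, the plan's rule gives 17.7% / 15.4% for a true risk of 20%, and 26.6% / 23.2% for 30%.

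**Step 4: BLRM.** Posterior P(rate > 30%) at a dose with 1 DLT, for 1/6, 1/5 and 1/4. The ratio is that dose divided by max(d). Ratio 1 is a bound, because Appendix C sets max(d) above the planned doses.

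| Ratio | That dose alone | With 0/6 at each of two lower doses (half and a quarter of the ratio; assumed) |
|---|---|---|
| 0.8 | 0.142, 0.188, 0.247 | 0.028, 0.037, 0.050 |
| 1 | 0.18, 0.24, 0.30 | 0.05, 0.07, 0.09 |

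Once lower cohorts are in the model, as SAP 9.6.2.1 requires, one or two losses barely move the result and it stays far from 0.25.

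**The case against.** The strongest reply is that the sections should be read together. The review meeting is held once all evaluable subjects have completed 4 weeks, and Appendix 3 bases escalation on data through the last subject's window. On that reading, completion is implied and SAP 6.2 is merely terse. This stands in part: the authors plainly expected completion. But those passages set the timing of a meeting. The analysis set is defined four times without the condition, and a programmer working from SAP 6.2 would include the subject.

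Several further points narrow the issue, and they stand:
- A subject who only stops drug is due a safety visit about 6 weeks after the last dose (Protocol 9.1.5), beyond day 28, and is not affected.
- A subject who dies within the window of a cause clearly unrelated to drug, observed until death, is a known non-DLT. Counting that subject as zero is correct.
- In the 2-weekly cohorts (1a, 3 and 5), two doses are all that fall due before day 29. What is missing there is follow-up, not dosing.
- Sites must try to trace lost subjects (Protocol 8.3), and serious events learned of later are still reported (Protocol 9.2.3.1.1.4), so some late DLTs could surface.

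It may also be said that the alternative set is no better. That is true of it alone: if 70% of the risk falls by day 8, it errs by 2.2 points with one loss against 1.2 for the plan's rule (27.2% and 23.8%, true 25%). This argues for showing both sets, not for replacing one with the other.

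**Conclusion.** The gap is real and minor. The definition lets a subject who leaves the study between dose 2 and the end of week 4 count as a full non-DLT, and the reported incidence can then only be equal or lower. It is lower only in a cohort with both a DLT and such a loss. In the constant-hazard example (cohort of 6, true risk 25%, loss after day 8), the expected understatement is 2.9 points with one loss (25 - 22.1) and 5.7 with two (25 - 19.3). These figures rest on assumed losses and assumed timing; the documents report neither.

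A reader might infer that the rule distorted the MTD or a dose decision, particularly since a single-dose fit at ratio 1 crosses the 0.25 limit when two subjects are left out (0.18 to 0.30). The documents do not support that. The final fit uses all evaluable subjects at all doses, no planned dose sits at ratio 1, the actual doses are redacted, the model runs only after a first DLT, and SAP 9.6.2.1 makes it non-binding. The study was also terminated early, with the expansion cohort and phase 2 cancelled (SAP 1 and 3.1). What remains is the accuracy of the reported DLT incidence and of any final MTD estimate.

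**What to change.** Keep the protocol-defined DLT set as primary, so that the primary-endpoint population does not change late in an open-label study. Add to SAP 6.2 and 9.6.2.1:

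1. By cohort, the number of subjects in the DLT set who left the study or were lost before the end of the 4-week window without a DLT.
2. If there are any, a repeat of the DLT table without those subjects, and of the final BLRM fit if one is run. Every subject with a DLT in the window stays in. A subject who died of a clearly unrelated cause and was observed until death stays in as a non-DLT.
3. A statement that the protocol set errs low and the second set errs high, with the DLT rate interpreted from both.

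If nobody was lost in the window, one sentence saying so is enough.

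The cost is a few lines of SAP text, one analysis flag, one count per cohort and, only if losses occurred, one repeated table and possibly one repeated fit. The downside is a smaller second set that tends to overstate the rate, which is why it stands beside the protocol set and does not replace it.
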